#### **6.5 Sample Size and Power**

For PROM development, 4-10 participants per item with an absolute minimum of 100 is often recommended for field testing. Therefore, this study will have 150 patients complete each module. Based on a host institution pilot study of 50 patients, the percentage of those being indicated for the IMPACT-N, IMPACT-O, and IMPACT-J were 40%, 30%, and 60%, respectively. Therefore, it is expected that 500 patients with maxillofacial trauma will need to be recruited in order to properly validate the least common IMPACT-O with at least 150 patients. The anticipated nonresponse rate from this pilot study was 33%, so it is expected that a total of 750 patients will need to be invited in order to meet this sample size.

### **7 SAFETY MANAGEMENT**

#### **7.1 Clinical Adverse Events**

Clinical adverse events (AEs) will be monitored throughout the study; however, this is an observational study that does not involve any medical care procedures so AEs are not expected.

#### **7.2 Adverse Event Reporting**

If any unanticipated problems related to the research involving risks to subjects or others happen during the course of this study, these will be reported to the institutional IRB where the incident took place.

---

## STUDY ADMINISTRATION

### 7.3 Data Collection and Management

Data collected in this study will be obtained in two formats: survey data and chart review data, as previously described.

#### 7.3.1 Data sources

Survey data source: This will be collected by a member of the research team during the patients regular scheduled visit. The goal is for this survey to be completed while the patient is in their exam room waiting for the physician or discharge paperwork so that no extra time is added to their visit. A member of the research team will identify the patient, obtain informed consent, and provide the IMPACT and 15D surveys to complete.

At the host institution, surveys will be collected via research tablets available in the clinic. The patient will be given a tablet that already has the appropriate IMPACT modules loaded based on their fracture pattern. They will complete the surveys electronically which will automatically save the data to their record on the encrypted, institutional REDCap database at each institution. Confidentiality will be prioritized as only members of the IRB-approved research team will have access to the REDCap for this study.

For centers where tablets are not available, the patient may completed the surveys on paper. A member of the research team will then transfer this to the REDCap afterwards and shred the paper data to minimize the risk of loss of confidentiality.

Chart review data source: The data listed above will be extracted from the medical record for every participant in this study. This will be performed privately by at least one member of the research team using a protected device with access to the electronic medical record.

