#### **4.1.2 Procedures: Follow-up Visit**

IMPACT and 15D Survey Completion: A member of the research team will assign and administer the appropriate IMPACT modules for each patient based their fracture pattern (preferably on a tablet, but may complete on paper if needed). Alternatively, patients will be

---

offered the opportunity to provide their email address to complete the follow-up survey at home at a later date.

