This table identifies the appropriate modules to administer to patients with varying patterns of facial trauma. Modules are designed to be assigned by the research team or trained clinical staff before the encounter. These modules function independently, where one patient may only qualify for the IMPACT (ie. soft tissue injury only) while another may warrant all four modules (ie. Le Fort III or panfacial fractures).

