#### 6.4.1 Baseline Data

The following chart review variables will be abstracted after informed consent is obtained and the initial survey is completed. This data will be summarized descriptively with average, median, range, interquartile range, and standard deviation, as appropriate. Each variable will then be tested for association with IMPACT scores on univariable analysis. Clinically or statistically significant variables will then be included in subsequent multivariable testing.

---

---

- Sociodemographic data: Age, sex, race, ethnicity, marital status, smoking status, payor type (private, medicare, Medicaid, government, none / self-pay, or other), and Social vulnerability index (SVI) values based on home address.
  - SVI: A measure of social vulnerability assigned to each zip code or census tract by the Center for Disease Control and Prevention.
- Trauma data: Mechanism, concomitant multisystem trauma, airway status, level of care (discharged from emergencet room, floor/stepdown admit, intensive care admit), presenting signs or symptoms (cranial nerve weakness, trismus, malocclusion, visual impairment), description of facial trauma, comprehensive facial injury (CFI) score, and Facial Injury Severity Score (FISS).
  - CFI: An objective scale based on maxillofacial imaging and clinical exam providing an integer that represents fracture severity by correlating it with the operative time for repairing each fracture.
  - FISS: An objective scale based on maxillofacial imaging and clinical exam providing an interger that represents the objective severity of facial trauma by correlation with the cost of management.
- Management data: Treatment (observation, bedside intervention, or surgical repair), type of surgical repair (closed reduction, open reduction, internal fixation, external fixation, and maxillomandibular fixation [MMF]), hospital length of stay (days), disposition (home versus medical facility)
- Objective complications: Wound infection or dehiscence, Malunion or nonunion, hardware extrusion, or any unplanned return to the emergency department, admission or reoperation related to the facial injury.
- Survey metadata: time from trauma to survey (days), time from intervention to survey (if applicable; days), presence of maxillomandibular fixation at the time of the survey.

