#### **6.4.4 Analysis of Secondary Outcomes of Interest**

1. IMPACT independent predictors: This secondary objective will identify independent variables that are associated with IMPACT scores. Multivariable logistic and linear regression models will be developed for categorical and continuous independent variables, respectively, and tested for association with each IMPACT score. Those independently associated with the IMPACT will be reported and factored into the multivariable regression for the primary endpoint.
2. Internal consistency and reliability will be measured by Cronbach alpha testing, item-response theory (IRT), and correlation between initial and followup surveys for patients completing both within one month.
3. The MCID for each module and subscale will be calculated using an anchor-based approach with a single item that addresses each patient's overall satisfaction.

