### **7.5.3 Potential Benefits of Study Participation**

Potential benefits are an additional opportunity for the patients to share symptoms and experiences while recovering from facial trauma, which may help the treating physician better understand how to care for each patient. This will also help contribute to an improved understanding of the recovery process after suffering facial trauma.

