## **7.7 Recruitment Strategy**

Potential participants identified in the screening phase above will be recruited while they are at a regular clinic follow-up. This will be performed by a member of the research team in a private setting, such as in the patient room while waiting for the clinician or clinic staff. If they agree to participate, they will be provided the tablet with the appropriate IMPACT modules uploaded (or appropriate pieces of paper). Informed consent will be obtained.

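### The survey may be completed before the consultation, after it or (at follow-up) at home, and the survey metadata do not record which, so retest and change results can absorb a difference in setting

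*Protocol*

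**What the plan says.** Section 7.3.1 gives a goal for when the survey is done: "completed while the patient is in their exam room waiting for the physician or discharge paperwork so that no extra time is added to their" appointment. Waiting for the physician comes before the consultation and waiting for discharge paperwork comes after it, so both are allowed.

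Section 4.1.2 adds a third condition, for the follow-up survey only. Patients may be "offered the opportunity to provide their email address to complete the follow-up survey at home at a later date".

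Section 6.4.1 lists what is recorded about each survey: "Survey metadata: time from trauma to survey (days), time from intervention to survey (if applicable; days), presence of maxillomandibular fixation at the time of the" questionnaire. No item says whether the clinician had been seen or whether the survey was done at home.

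Two secondary analyses compare a patient's two surveys. Section 6.4.4 assesses reliability partly by "correlation between initial and followup surveys for patients completing both within one month", and Section 6.2 lists the change in IMPACT scores at later visits as an endpoint.

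**The concern.** A consultation can change how a patient answers the same day. Examination, a bedside procedure or news about recovery may move answers on pain, function or worry. If one survey is done before the encounter and the other after it, or at home, that movement enters the comparison of the two. The retest correlation then reads it as unreliability, and the change analysis reads it as change.

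The order is unlikely to be random:

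- Sections 3.2.1 and 5.1.1 put the IMPACT at 2 to 20 minutes depending on fracture pattern, so longer surveys are more likely to run past the clinician's arrival.
- Written consent is taken at the initial visit only (Section 7.8.1), which lengthens that visit and not the second.
- The at-home option exists only at follow-up, so any use of it makes the mix of conditions differ between the two surveys.

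Unrecorded order cannot be reliably rebuilt later. Day counts do not separate before from after on the same day. Paper forms are entered afterwards and shredded (Section 7.3.1), so entry time would not show completion time.

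**Working it through.** **Does another section settle the order?** No.

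- Section 5.1.1 says "Modules are designed to be assigned by the research team or trained clinical staff before the encounter". That governs which modules a patient gets, not when they are answered.
- Section 6.3 offers privacy during completion and does not address the moment in the visit.
- Section 7.7 describes the setting for recruitment, by way of example.

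**The plan's own figures.** The protocol gives no figure on this point. Its computed figures, in Section 6.5, do not depend on it: 150/0.30 = 500 to recruit, and 500/(1 - 0.33) = 746.3, rounded up to 747, against 750 stated (750 exactly if nonresponse is one third). Nothing here changes them.

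**Illustration (all inputs assumed).** Take a score with unit variance. Let a share q of surveys be done after the encounter, each shifted by d SD. The added variance is v = q(1 - q)d².

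*Retest correlation*, true value 0.85, order independent between the two visits: r = 0.85/(1 + v).

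| q | d | v | Retest r |
|---|---|---|---|
| 0.3 | 0.2 | 0.21 × 0.04 = 0.0084 | 0.843 |
| 0.3 | 0.5 | 0.21 × 0.25 = 0.0525 | 0.808 |
| 0.5 | 0.2 | 0.25 × 0.04 = 0.0100 | 0.842 |
| 0.5 | 0.5 | 0.25 × 0.25 = 0.0625 | 0.800 |

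From a true value of 0.80 with q = 0.5, the results are 0.792, 0.782 and 0.753 for d = 0.2, 0.3 and 0.5.

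The fall depends on order varying within patients. If each patient kept the same order at both visits, the shift would be shared and r would not fall: (0.85 + 0.0625)/(1 + 0.0625) = 0.859.

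*Share of pairs with different order*: 2q(1 - q) = 2 × 0.21 = 42% for q = 0.3, and 2 × 0.25 = 50% for q = 0.5.

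*Mean change*: bias = (q2 - q1)d, where q1 and q2 are the after-encounter shares at the first and second survey.

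- Equal shares (q1 = q2): bias 0.
- 20% then 50%: 0.3 × 0.2 = 0.06 SD to 0.3 × 0.5 = 0.15 SD.
- 20% then 60%: 0.4 × 0.2 = 0.08 SD to 0.4 × 0.5 = 0.20 SD.

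The sign reverses if the after-encounter share is higher at the first visit, which the consent step could cause. Unlike sampling error, this bias does not shrink with more patients.

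**The case against.** The best defence is practical. The sentence in Section 7.3.1 states a goal with a reason: no time is added to routine visits. In an observational survey that is a legitimate feasibility choice, and a mandatory slot before the encounter for consent, up to 20 minutes of IMPACT and the 15D would work against it. No document supports any particular visit effect or after-encounter share, and item recall periods, on which a same-day effect depends, are not shown. The choice of retest pairs may also be left to the SAP. All of this stands. It argues for a default where feasible and against a rigid rule or discarding pairs. It does not answer the missing field, because an analysis plan cannot use what was not collected.

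A reader might infer three stronger points. The documents do not support them.

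- **That the protocol contradicts itself on timing.** Section 7.7 suggests recruiting "in the patient room while waiting for the clinician or clinic staff", as an example of a private setting. Section 7.5.3 says answers may be shared in a way "which may help the treating physician better understand how to care for each patient", which is a general benefit statement. Neither fixes when the survey is completed, so neither conflicts with Section 7.3.1.
- **That the fixation covariate is misclassified.** Section 6.4.1 already defines it as "presence of maxillomandibular fixation at the time of the survey". An error could arise only if, on a day when fixation changes, the abstractor relied on the chart alone. The protocol does not say that this happens.
- **That the primary correlation is inflated.** The effect is small and can go either way. With the same q and d, a true r of 0.35 becomes (0.35 + v)/(1 + v) = 0.36-0.39 if both instruments shift equally, but 0.35/√(1 + v) = 0.34-0.35 if only the IMPACT shifts. With 150 patients, the 95% interval around 0.35 is about 0.20 to 0.48. If the visit truly alters pain or worry and both instruments register it, that is variation in quality of life, which is what they are meant to measure.

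**Conclusion.** The point holds as a cheap improvement of minor to moderate weight. Completion before the encounter, after it or at home (follow-up only) is permitted, the listed metadata do not record which applied, and the retest and change analyses depend on the two surveys being comparable.

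The size cannot be taken from the documents. With shifts of 0.2 to 0.5 SD, 30-50% of surveys after the encounter and order independent between visits, all assumed, the effect on the retest correlation is small to modest (0.85 to 0.80-0.84). Mean change is affected only if the mix differs between the two surveys. It is then the more exposed result, at 0.06 to 0.20 SD under the assumed swings. No sample size changes, and no finding is made against the primary endpoint.

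**What to change.** - **Section 7.3.1:** make completion of the IMPACT and 15D before the clinician encounter the default for in-clinic surveys at both visits, where feasible, at all sites.
- **Section 6.4.1:** add one survey-metadata field with three values (before encounter, after encounter, at home), filled in when the survey is completed.
- **Section 6.4.4:** use that field as a covariate or in a sensitivity analysis for the retest and change results. Keep all pairs in the main analysis. Excluding discordant pairs could lose 42-50% of them under the assumed shares, on top of the one-month limit, and would leave at-home surveys without a clear place.

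The cost is a sentence in 7.3.1, a REDCap field and a line in the analysis. Some surveys will still be completed or finished after the encounter, and these are flagged. The change concerns the timing of the questionnaire only and does not touch care.

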#### 7.3.2 Multi-institutional Data Management

Absolutely no identifying or other protected health information will be shared across research sites. Once the appropriate sample size has been achieved, the REDCap data at each institution will be deidentified and exported to an excel file. A single “record ID” interger with no identifying information will be assigned for each participant. This deidentified spreadsheet will then be sent via encrypted email to the host institution research team for aggregation and deidentified final analysis.

### 7.4 Confidentiality

All data and records generated during this study will be kept confidential in accordance with Institutional policies and HIPAA on subject privacy and that the Investigator and other site personnel will not use such data and records for any purpose other than conducting the study. To protect confidentiality, all data will be stored and managed electronically with each institutions password-protected, Research Electronic Database Capture (REDCap) software. A unique record ID interger will be assigned to each participant at an institution. No identifying information will be exported at any point within the study.

---

---

## **7.5 Regulatory and Ethical Considerations**

### **7.5.1 Data and Safety Monitoring Plan**

The institutional PI at each study site will monitor and review the study progress, subject safety, and the accuracy and security of the emerging data.

### **7.5.2 Risk Assessment**

Risk assessment will be performed by each participating institution. At the host institution, the research activities present were determined to pose no more than minimal risk to human subjects. Potential risks include loss of confidentiality, addressed above, and risk of feeling uncomfortable when taking the survey. This is addressed by ensuring the survey is optional and explaining that some questions may be uncomfortable. Patients may stop the survey at any time or skip items to minimize this risk.

### **7.5.3 Potential Benefits of Study Participation**

Potential benefits are an additional opportunity for the patients to share symptoms and experiences while recovering from facial trauma, which may help the treating physician better understand how to care for each patient. This will also help contribute to an improved understanding of the recovery process after suffering facial trauma.

### **7.5.4 Risk-Benefit Assessment**

Given the low-risk nature of this survey study, the benefits described above are expected to outweigh the potential risks.

## **7.6 Screening Strategy**

One member of the research team will screen patients on the upcoming clinic schedule to look for potential participants based on the “chief complaint”. Those with a chief complaint related to maxillofacial trauma will be reviewed for inclusion and exclusion criteria. If satisfied, a REDCap file will then be generated for that patient and the appropriate IMPACT modules will be selected. Patients that do not satisfy inclusion and exclusion criteria based on chart review will not be included and no information will be recorded.

## **7.7 Recruitment Strategy**

Potential participants identified in the screening phase above will be recruited while they are at a regular clinic follow-up. This will be performed by a member of the research team in a private setting, such as in the patient room while waiting for the clinician or clinic staff. If they agree to participate, they will be provided the tablet with the appropriate IMPACT modules uploaded (or appropriate pieces of paper). Informed consent will be obtained.

## **7.8 Informed Consent/Accent and HIPAA Authorization**

### **7.8.1 Main Study**

All patients who agree to participate will be asked to provide written consent in person during the initial visit. Each institution will use the consent form approved by their institutions IRB.

---

### **7.8.2 Individuals with Limited English Proficiency**

Patients unable to read English will be excluded. Once this survey has been properly validated in its original English language, it be translated and tested in other languages (future research); however, translating this in one language is a necessary first step.

### **7.8.3 Waiver of HIPAA Authorization**

HIPPA authorization for collection of chart review data will be obtained during the consent process at each participating institution.

## **8 PUBLICATION**

Only aggregate data without individually identifiable information will be published. All participating research authors will review and provide edits to the final submission.

---

---

